#### **7.1.4 Data Protection and Verification**

No participant names will be used but rather only client ID numbers. The codes that link the name of the participant and the study ID will be kept confidential by the PI and UNM Project related staff and students and will be stored on the secure CASAA network. In addition, we have a Certificate of Confidentiality. If for some reason there is a breach of confidentiality, an adverse event will be reported to all required parties.

The Quality Assurance (QA) Monitor ([name]) will visit the Southwest Native American tribe on a monthly basis to review research form completion and provide feedback to the RA on assessment completion. The QA Monitor will note any protocol violations in the Protocol Violation Log.

#### **7.2 Data Entry and Transfer**

All data will be double-entered in separate databases to prevent data entry errors. Data will be entered at the Southwest Native American MICRA offices first by the research assistant at Southwest Native American tribe on a desktop, and then double entered by a UNM MICRA team member trained in data entry. Once the data is entered, the two records will be compared electronically to identify discrepancies. The hard copy of the data will be reviewed to determine which entered value was correct. Discrepancies will be corrected by a supervisor based on source documents with notations and initials on the source documents if necessary. This procedure has been shown to result in less than one entry error per 10,000 (as compared with 3-5% error on single pass data entry by research assistants).

In order to transport these data to UNM from the Southwest Native American tribe, a VPN connection will be set up by CASAA's Information Technologist [name]. The deidentified data file will be saved to the PI's private Novell drive and will be backed up as part of CASAA's routine weekly back-up system. [name]. is the statistician on this grant, so he will have access. Anyone else needing access would require PI permission to conduct data analyses or work on poster presentations and manuscripts. There will be one data file with identifying information: (1) the link between participant names and study ID numbers. This datafile will be password protected on the PI's private Novell drive at CASAA.

#### **7.4 Data Ownership**

The MICRA data belongs to the Southwest Native American people, and the Southwest Native American Tribal Council must approve all publications and presentations within a timely manner prior to outside release. National Institute of Drug Abuse and University of New Mexico Human Research Review Committee officials reserve the right to audit the data files to ensure compliance with research procedures. To protect participant confidentiality, the forms linking participant names to data forms will not be shared with the Tribal Council and only the PI, Co-PI and RA will have access to these linking

documents during the study. The link between names and research data will be destroyed once all data has been entered and verified. The hard copies of the data will remain in the Southwest Native American tribe at the Tribal Recovery Center in locked file cabinets. The director of the Southwest Native American Tribal Recovery Center ([name]) and the tribal council administrator will be provided with file cabinet keys, and individuals wishing to access the data must complete a MICRA file access log. Hard copies of the data will be destroyed five years after all tribally-supported publications have been published. The study PI will keep an electronic copy of the data, and the Tribal Council will also retain an electronic copy of the data.

### **7.5 Data Analysis Plan**

The primary dependent measure of use derived from the Form 90 and the saliva drug tests will be percent days abstinent from: alcohol, amphetamine, cannabis, cocaine, and inhalants. Secondary outcomes measures include other self-report assessments such as self-reported days of substance use and oral saliva drug results, self-efficacy, negative consequences, cultural identity, microaggressions and sexual risk behaviors. Outcome data will be analyzed using two-group MANOVA comparing MICRA and TAU conditions on key dependent measures: (1) percent days abstinent from all substances of abuse as measured from timeline follow-back, and (2) level of substance related problems as measured by the InDUC. The endpoint for this analysis will be 4-month follow-up and baseline levels of the dependent measures will be entered as covariates. Later analysis will explore outcomes across 12 months post-randomization. Secondary analyses will employ hierarchical linear modeling (HLM) for modeling effects over time given we have at least 3 time points. Exploratory analyses will also encompass outcomes on secondary measures such as ASI, cultural identity, microaggressions, brief symptom inventory, and sexual risk behaviors. Alpha level will be set at .05. The study's statistician or PI will analyze these data using SPSS software and Amos.

*Appendix A*

**SOUTHWEST NATIVE AMERICAN MICRA PROJECT  
[name]  
[name]**

**REFERRAL/ASSESSMENT REPORT**

**Date:** \_\_\_\_\_

**Client's Name:** \_\_\_\_\_ **Referral Date:** \_\_\_\_\_

**Referring Agency:** \_\_\_\_\_ **Cause#:** \_\_\_\_\_

**Date of Intake:** \_\_\_\_\_ **Date of Assessment:** \_\_\_\_\_

**Date Case Staffed:** \_\_\_\_\_

**Assigned Counselor:** \_\_\_\_\_

**Recommended Treatment Plan:**

*Client is receiving outpatient treatment services with the Southwest Native American MICRA Project*

**Outpatient Treatment Services to be provided by Southwest Native American MICRA Project:**

- 1.
- 2.
- 3.

**Referrals to be made:**

**Counselor's Signature:** \_\_\_\_\_ **Date:** \_\_\_\_\_

**Clinical Supervisor:** \_\_\_\_\_ **Date:** \_\_\_\_\_

**cc: Client/file/Client management/Referring agency**

## *Appendix B: Phase I Sample Screening Script*

(Assessment process can be interpreted in the Southwest Native American Language if participant does not fully understand English)

Good Morning/Good Afternoon. My name is [name], I am the research/administrative assistant with the Southwest Native American MICRA Project. I am the person who collects research data before, during and after treatment in order to evaluate the effectiveness of treatment. I will be the person in charge of doing the screening and consent process, the baseline as well as the 4 and 8 month follow up visits. Thank you for coming in today. I really appreciate your patience in getting together to meet with one another. It shows how much determination you have to help yourself. I understand you have expressed interest to participate in the Research study and that we have received your referral from the Southwest Native American Recovery Center.

We will be starting out by doing the screening & consent process to determine if you are eligible for the study. It will take at least an hour to do the necessary paperwork to determine your eligibility. Do you have any questions before we proceed?

Let's start out by discussing a little bit about the study. May I share with you what the MI/CRA Study is about? Southwest Native American Pueblo in collaboration with the University of New Mexico has teamed up to do a research study to see if Motivational Interviewing (MI) and Community Reinforcement Approach (CRA) will work for our Southwest Native American People. This is a non-confrontational and strengths based model that focuses on building motivation for change. We provide outpatient substance abuse counseling and with your permission we would like to pay you for your participation in the research study which will be in the form of a gift certificate after the initial intake interview and cash incentives at 4, and 8 month follow-ups. We will not force you to stay in the study if you do not wish to continue and we will honor and respect your decision. I would also like to inform you that I will not be in charge of your treatment process as you will be working one on one with a counselor here within the MICRA Project and that all information obtained from you during your follow up assessments will not be shared with your counselor but Baseline information may be shared for feedback purposes.

Do you think this study might be something you're interested in? (Depending on whether the client is interested...) Wonderful that you would like to take part in the research study. The next step is to determine if you would be eligible to take part in the study, but first we would need to do an alcohol breathalyzer test before we proceed. Each participant who agrees to continue with the screening is asked to voluntarily provide us with a BAC. Your BAC information will not be shared with your referring source; again your information will be kept confidential. With your permission, I would like to administer the BAC. (If BAC is beyond .05, then participant must be informed that their BAC is higher than expected and reschedule the Screening and Consent Process to another date and time.)

Another important item I would like to stress is that all information gathered while participating with the project will be kept confidential and the only time any

information can be released is if you give us permission by signing a Release of Information Form.

Next we will be completing a form about your alcohol and drug use. It will take approximately 30 minutes to complete. I will be asking you questions that pertain to alcohol or substance use within your lifetime. (After completing the SCID, the RA will determine whether the participant meets the eligibility criteria for substance abuse or dependence. If participant is eligible, the Consent form can be explained more in depth and questions will be answered if the participant has any prior to signing the form. The HIPAA Form will be signed during this time.)

(After all screening documents have been completed) Thank you for coming in today to complete all the necessary paperwork to determine your eligibility for this Research Study. Since you have decided to participate in this study I will go ahead and schedule an appointment for you to come back in and do the entire assessment process, unless you have time to complete some of the forms today? (Depending on yes or no) Do you have any questions or concerns pertaining to anything we discussed today or anything relating to the study? (Hand participant appointment slip for assessment process) Thank you once again for coming in today and hope to see you on your next scheduled appointment. Take care! Elahkwa.

### *Appendix C: Phase II Sample Screening Script*

(Assessment process can be interpreted in the Southwest Native American Language if participant does not fully understand English)

Good Morning/Good Afternoon. My name is [name], I am the research/administrative assistant with the Southwest Native American MICRA Project. I am the person who collects research data before, during and after treatment in order to evaluate the effectiveness of treatment. I will be the person in charge of doing the screening and consent process, the baseline as well as the 4, 8, and 12 month follow up visits.

Thank you for coming in today. I really appreciate your patience in getting together to meet with one another. It shows how much determination you have to help yourself. I understand you have expressed interest to participate in the Research study and that we have received your referral from the Southwest Native American Recovery Center.

We will be starting out by doing the screening & consent process to determine if you are eligible for the study. It will take at least an hour to do the necessary paperwork to determine your eligibility. Do you have any questions before we proceed?

Let's start out by discussing a little bit about the study. May I share with you what the MI/CRA Study is about? Southwest Native American Pueblo in collaboration with the University of New Mexico has teamed up to do a research study to see if Motivational Interviewing (MI) and Community Reinforcement Approach (CRA) will work for our Southwest Native American People. This is a non-confrontational and strength based model that focuses on building motivation for change. You will receive outpatient substance abuse counseling and with your permission we would like to pay you for your participation in the research study which will be in the form of a gift certificate after the initial intake interview and cash incentives at 4, 8, 12 month follow-ups. We will not force you to stay in the study if you do not wish to continue and we will honor and respect your decision. I would also like to inform you that I will not be in charge of your treatment process as you will be working one on one with a counselor and that all information obtained from you during your follow up assessments will not be shared with your counselor but baseline information may be shared for feedback purposes.

There are two programs participating in the study, the MICRA project and Southwest Native American Recovery Center. If we find that you are eligible for the study, we will put your name in a randomization program which means you will receive your treatment services either with MICRA or Southwest Native American Recovery Center. The purpose of randomization is to make sure that the groups of participants who receive the two treatments are balanced in terms of things like age, education, etc. I will not know which treatment you will receive, and you must be okay with not knowing which treatment you will get. Do you have questions about the randomization process? If you are assigned to SWNARC we will not lose all contact with you. I will continue to stay in touch with you by doing follow ups and to provide you with your incentives.

Do you think this study might be something you're interested in? (Depending on whether the client is interested...) Wonderful that you would like to take part in the

research study. The next step is to determine if you would be eligible to take part in the study, but first we would need to do an alcohol breathalyzer test before we proceed. Each participant who agrees to continue with the screening is asked to voluntarily provide us with a BAC. Your BAC information will not be shared with your referring source; again your information will be kept confidential. With your permission, I would like to administer the BAC. (If BAC is beyond .05, then participant must be informed that their BAC is higher than expected and reschedule the Screening and Consent Process to another date and time).

Another important item I would like to stress is that all information gathered while participating with the project will be kept confidential and the only time any information can be released is if you give us permission by signing a Release of Information Form.

Next we will be completing a form about your alcohol and drug use. It will take approximately 30 minutes to complete. I will be asking you questions that pertain to alcohol or substance use within your lifetime. (After completing the SCID, the RA will determine whether the participant meets the eligibility criteria for substance abuse or dependence. If participant is eligible, the consent form can be explained more in depth and questions will be answered if the participant has any prior to signing the form. The HIPAA Form will be signed during this time).

(After all screening documents have been completed) Thank you for coming in today to complete all the necessary paperwork to determine your eligibility for this Research Study. Since you have decided to participate in this study I will go ahead and schedule an appointment for you to come back in and do the entire assessment process, unless you have time to complete some of the forms today? (Depending on yes or no) Do you have any questions or concerns pertaining to anything we discussed today or anything relating to the study? (Hand participant appointment slip for assessment process) Thank you once again for coming in today and hope to see you on your next scheduled appointment. Take care! Elahkwa.

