### 1.4.4 Treatment as Usual

Southwest Native American Recovery Center (SWNARC), the sole outpatient substance abuse treatment program in the Southwest Native American tribe, will serve as the treatment as usual (TAU) comparison for this study. Treatment provided by the Southwest Native American Recovery Center is fairly consistent in its approach. The intake staff assess all clients. Detailed histories are gathered, individual cases are staffed, and clinical assignments are made. Clients are assigned to counselors who have openings; there is no attempt to match client to counselor, other than with an eye towards gender. Treatment starts with individual sessions. Soon thereafter the client joins ongoing group sessions. The clinical staff usually runs group sessions (90 minutes on average), and they engage clients with a reflective style, encouraging them to share their stories regarding substances. Newer group members are generally quiet. From time to time, elder Southwest Native Americans will come to the group meeting and discuss either their personal struggle with substance abuse, or share Southwest Native American perspectives on treating all things - including the self- with respect. Examples of ongoing groups

include a men's group, women's group, arts and crafts group, and Triple A dance group. Individual counseling sessions (60 minutes on average) consist of listening and implementing a generally didactic style that compares current behavior with desired behavior, current situation with optimal situation. Individual sessions occur once weekly, but may happen more frequently if an individual is in crisis. 12 step principles are presented at SWNARC, but more in spirit than in substance. Family members are usually not included in counseling sessions. Individual sessions also review Southwest Native American traditional teachings, showing the client his or her place within the framework of Southwest Native American life. Three cultural educators are part of the SWNARC staff. Release from substance abuse treatment is based on clinical judgment. While clients can spend up to a year at SWNARC, the average length of treatment is two months.

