### **3.3 Identifying Potential Participants**

Participants primarily will be recruited through Southwest Native American Recovery Center (SWNARC). The SWNARC intake technician, [name] will approach all individuals who come to SWNARC for treatment and briefly discuss the study with them to assess their level of interest. If a SWNARC staff member other than the intake technician completes the intake, they will also tell the individual about the study. This discussion will take place in a private room, after the potential participant has completed the intake papers and the SASSI. Individuals with multiple questions about the study will be encouraged to contact the MICRA research assistant. Occasionally individuals may enter the MICRA offices and inquire about the study without first going to SWNARC. When this happens, they will be given a pamphlet, a brief explanation of the MICRA Project, and referred to the intake technician at SWNARC to begin the intake and recruitment process. MICRA counselors will also give presentations at the Southwest Native American Detention Center explaining the MICRA study to detainees, but individuals must still go through SWNARC as the single point of entry to become enrolled in the study. Many individuals from the Southwest Native American detention center are subsequently referred to SWNARC, so these presentations will help to raise awareness about the study.

All interactions with potential participants will be recorded in the SWNARC Screening Log. The Screening log reports gender, whether individuals were approached for and/or interested in the study, action taken post-study discussion. Tracking updates will be e-mailed to [name], the CASAA RA, on the 1st and 15th of the month. There are some cases where individuals who come into SWNARC will not be approached for the study (although these individuals must be included in the SWNARC tracking log):

- Major cognitive impairment, actively psychotic, or chronic mental illness not well-treated, as assessed by SWNARC staff/the Co-I [name].
- The individual requires more intensive detoxification services and is referred out of SWNARC (they can be approached for the study post-detox).

- Basic exclusion criteria are evident: The individual is under 18, not Southwest Native American, does not speak English, is not willing to be randomized (for Phase II), or does not live within the required area.

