**Table 6.1 Enrollment, Treatment, and Follow-up Risk Factors**

Enrollment Phase Risk Factors:	Treatment Phase Risk Factors:	Follow-Up Phase Risk Factors:

Expressed
 
 
• Concerns about randomization
 
• Expectations for being assigned a specific treatment
 
• Concerns with one or some aspects of the study protocol
 
• Other expressed enrollment risks
 
 
Observed
 
 
• Rescheduled screening appointments
 
• No-show for screening appointments
 
• BAC>0 at baseline interview
 
• Problems with detoxification
 
• Permanent address is different from current address
 
• Duration of current address is less than 3 months
 
• Plans to move in the next year
 
• Other observed enrollment risks
 
	
Expressed
 
 
• Dissatisfaction with treatment assignment
 
• Dissatisfaction with treating clinician(s)
 
• Difficulty to meet time demands
 
• Other expressed treatment risks
 
 
Observed
 
 
• Rescheduled treatment appointments
 
• No-show for treatment appointments
 
• Unresponsive to or refusing routine scheduling procedures
 
• Manifestation of clinical deterioration
 
• Early drop out from treatment
 
• Plans to move in the next year
 
• Loss of housing
 
• Unexpected social, occupational, or health event
 
• Lost contact (disconnected phone or out of minutes, undelivered mail)
 
• Other observed treatment risks
 
	
Expressed
 
 
• Dissatisfaction with services provided
 
• Dissatisfaction with treating clinician(s)
 
• Difficulty to meet time demands
 
• Other concerns expressed during follow-ups
 
 
Observed
 
 
• Loss of interest in the study due to end of treatment
 
• Clinical deterioration
 
• Plans to move in the next year
 
• Loss of housing
 
• Unexpected social, occupational, or health event
 
• Other observed follow-up risks
 

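### The Phase II sample screening script describes only MI/CRA, in favourable terms, and reassures only about SWNARC, an avoidable risk of unequal expectations in an unmasked trial whose 4-month outcomes rest largely on participant report

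*Protocol*

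**What the plan says.** Appendix C of the protocol is the sample script that the RA uses with Phase II candidates before consent and randomization. It presents the study as finding out whether MI and the "Community Reinforcement Approach (CRA) will work for our Southwest Native American People", and says of that treatment: "This is a non-confrontational and strength based model that focuses on building motivation for change". It tells every candidate that "you will be working one on one with a counselor". SWNARC is introduced only by name, as the other participating program. After explaining randomization the script adds: "If you are assigned to SWNARC we will not lose all contact with you", followed by a promise of follow-ups and incentives. No matching sentence covers assignment to MICRA.

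Section 1.4.4 describes SWNARC care. Treatment begins with individual sessions, then "Soon thereafter the client joins ongoing group sessions". Individual work continues: "Individual sessions occur once weekly, but may happen more frequently if an individual is in crisis". Visiting elders and three cultural educators are also part of the program.

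Section 3.3 adds an outreach channel: "MICRA counselors will also give presentations at the Southwest Native American Detention Center explaining the MICRA study to detainees". Entry to the study still runs through SWNARC.

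**The concern.** What people are told just before randomization shapes what they expect from each arm. Here one arm has a favourable description and the other has a name and a reassurance. Randomization does not remove an effect of this kind, because the expectation acts after assignment is known. It could affect whether people start treatment, whether they stay, and what they report.

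Aim 4 is to estimate effect sizes for MICRA. Any shift caused by unequal expectations would be added to that estimate and could carry into the planning of a larger trial. The protocol recognises the general mechanism: its table of enrollment, treatment and follow-up risk factors (Table 6.1, section 6.2.3) lists expectations of a specific treatment and "Dissatisfaction with treatment assignment" among factors that may accompany non-adherence.

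**Working it through.** The protocol states no power calculation, SD or expected effect size, so there is no figure of its own to reproduce. The check is mainly a comparison of texts.

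**What the script tells candidates about each arm**

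| Element | MICRA | SWNARC |
|---|---|---|
| Description of treatment | Yes, favourable | None |
| Format | One on one | One on one; groups not mentioned (compare 1.4.4) |
| Stay-in-touch reassurance | None | Yes |
| Statement that the better program is unknown | None | None |

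A likely origin is visible. The Phase II text largely reuses the single-arm Phase I script (Appendix B). There the one-on-one sentence placed the counselor in the MICRA Project. Phase II dropped that phrase and kept most of the rest.

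**Can unequal expectations reach the outcomes?**

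- Masking: the RA opens the envelope and tells the participant the assignment (4.5). The script has the same RA do the 4-, 8- and 12-month visits.
- Outcomes: the 4-month MANOVA uses percent days abstinent from calendar recall and the InDUC (7.5). The InDUC is a self-report questionnaire (4.4.1).
- Objective checks: section 7.5 also names saliva tests in the primary measure, and oral fluid and breath alcohol are collected at each follow-up. The oral fluid panel (4.2.2) covers neither alcohol nor inhalants, two of the five target substances. A breath reading covers alcohol at the visit, not the months before it. These are a partial check.
- Non-starters: randomized people who do not begin treatment are not replaced (3.1) and are still invited to the research assessments (3.5), so a difference in starting stays in the comparison.

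**Scale, as illustration only**

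Inputs from the protocol: 40 per arm (5.1); a follow-up aim of at least 80% (6.1), so 0.80 × 40 = 32 per arm; alpha .05 (7.5), taken as two-sided. Assumed input, with no source in the protocol: a shift b, in SD units, against SWNARC with no true effect.

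- SE of the standardized difference = √(2/n): √(2/40) = 0.224; √(2/32) = 0.250.
- Chance of a significant result favouring MICRA = P(Z > 1.96 − b/SE).

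| b | 40 per arm | 32 per arm |
|---|---|---|
| 0 | 2.5% | 2.5% |
| 0.1 | P(Z > 1.51) = 6.5% | P(Z > 1.56) = 5.9% |
| 0.2 | P(Z > 1.07) = 14.3% | P(Z > 1.16) = 12.3% |
| 0.3 | P(Z > 0.62) = 26.8% | P(Z > 0.76) = 22.4% |

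If the SD of percent days abstinent were 30 points (also assumed), 0.1 to 0.2 SD would be 3 to 6 points. Such a shift is 0.1/0.250 = 0.4 to 0.2/0.224 = 0.9 standard errors, too small to be recognised in the trial's own data. This is a single-outcome, unadjusted approximation, not the planned two-outcome MANOVA with baseline covariates.

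**The case against.** The strongest reply is that the harm is not shown, and much of that reply stands.

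- A reader might infer that SWNARC participants start out disappointed. Nothing in the protocol says so. The risk-factor table is generic and is not evidence about this script.
- A reader might say the script misstates SWNARC care. The one-on-one statement is incomplete rather than false, because SWNARC clients have weekly individual sessions. In context it mainly separates the RA's role from the counselor's.
- A reader might see the SWNARC-only sentence as consolation. It can equally be read as a retention message from MICRA staff to people who may be treated elsewhere. What stands is that it is given for one arm only.
- A reader might say MICRA counselors promote their own arm in detention. The protocol speaks of explaining the study and raising awareness, and it gives no tilted content. It does not say how many participants first hear of the study there.
- Candidates come to SWNARC for treatment and normally hear of the study first from its own intake staff. Those unwilling to be randomized are not approached (3.3). This makes a strong prior pull toward MICRA less certain, but it does not balance the script.
- Appendix C is a sample. Section 3.4.7 requires discussion of concerns and alternatives. The consent pages and some handout pages are not available here, so a balanced description there cannot be excluded. The script still comes before consent and asks for interest on its own description.
- Knowledge of assignment is unavoidable, so neutral wording would not remove every expectation effect. It would remove the part that the script adds.

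**Conclusion.** The point holds as an imbalance in the sample script and an avoidable risk of bias. That the script describes only MI/CRA, omits SWNARC's groups, reassures about one arm and does not say that the better program is unknown can be read directly from Appendix C and section 1.4.4. That this could reach the Aim 4 estimate follows from the unmasked participants and RA and from outcomes resting largely on participant report, with oral fluid and breath tests as a partial check.

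The direction is probably towards MICRA. The size is unknown. The 6-14% range applies only to an assumed shift of 0.1 to 0.2 SD with 32 to 40 per arm, and nothing in the protocol ties the wording to a shift of that size. The case for revision rests on the visible asymmetry and the low cost of correcting it, not on that figure.

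**What to change.** Revise Appendix C as follows:

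- Give two short descriptions, of MICRA and of SWNARC, equal in length and tone. The SWNARC one should mention its groups as well as its individual sessions.
- State that it is not known which program works better.
- Replace the SWNARC-only sentence with one for both arms: whichever program the person is assigned to, the RA will stay in touch for the 4-, 8- and 12-month interviews.
- Use the same neutral text in the detention-center presentations. Moving those talks to the RA is not clearly better, because the RA is also MICRA staff and the unmasked assessor.

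If any false-positive figure is cited, label it as illustration. The cost is an IRB-approved wording change and a slightly longer script.
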